4 STUDY DESIGN

4.1 OVERALL DESIGN

Hypothesis (Aim 1): The treatment group will show greater improvements in daily activity and sedentary behavior outcomes than controls after 16 and 24 weeks.

Hypothesis (Aim 2): The treatment group will show greater improvements in health and psychosocial outcomes than controls after 16 and 24 weeks.

Phase: 1A.

Design: Randomized control trial

Participant assignment: 1:1 Simple Randomization conducted by graduate assistant

Number of study group: 2 (control/treatment); intervention period= 4 months; follow-ups after 4 and 6 months.

Number of sites= Single site trial.

Name and description of intervention: Companion; An integrated system of wearable sensors and the smartphone. It is a behavior-aware, virtual “Companion” that uses a “human-in-the-loop” approach to enable meaningful two-way communication. Companion builds rich models of typical behavior using sensors and context sensitive ecological momentary assessment (CS-EMA) to deliver intervention components and behavior change strategies using socially engaging, contextually salient, and tailored text-message conversations in near-real-time.

Description of control group: This group will not receive the Companion, which will be the only difference with the treatment group. I.e., the control group will receive standard treatment– the supervised training program and an exercise prescription for those days without supervision.

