Control Group: This group will not receive the Companion, which will be the only difference with the treatment group. I.e., the control group will receive standard treatment– the supervised training program and an exercise prescription for those days when they are on their own. This will be done on the two days when control group participants meet face-to-face with the trainer for supervised training.

Primary Outcomes: Total duration and number of bouts of: (i) light and moderate-to-vigorous physical activity and (ii) sedentary behavior measured over a period of one week using accelerometry.^{38,39} Week-long measures will be made at baseline, and weeks 16 and 24.

Exploratory Outcomes: Cardiometabolic health: Plasma glucose, HbA1C, insulin, and lipids. Body composition: lean and fat mass. Physical function. Muscular and aerobic fitness. Cognition.⁴² Perceptions of competence related to health behaviors. Autonomy support (from companion). Autonomous motivation (for physical activity). Relatedness (to the Companion). General satisfaction.

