(ii) Aerobic Fitness- We will assess aerobic fitness using the 6-minute walk test. This is a simple test that requires no specialized equipment and only requires the participant to walk on a flat, hard surface for a period of 6 min. The total distance walked during this duration is measured using a measuring wheel.

8. Other: (i) 7-14 days after baseline, participants in the general exercise intervention group will have a virtual 30-min face-to-face counseling session with the researchers on: i) benefits of reducing sedentary behavior and increasing physical activity, and ii) various strategies to decrease workplace and home sedentary behaviors and initiate a physically active lifestyle.

(ii) Participants in the lifestyle physical activity intervention group will have a virtual 60-min face-to-face counseling session via a HIPAA complaint ZOOM session. This session will include the same components received by the general exercise intervention group supplemented with an additional 30-min of conversation to further personalize his or her physical activity prescription plan and create goals related to physical activity and sedentary behavior lifestyle choices. During this time the researcher will ask the participant in the lifestyle physical activity intervention group questions about his or her schedule, preferences, health-related behaviors, and other behaviors related to work schedule, hobbies/leisure interests, family dynamics, home and work environment, means of daily transportation, etc. that can be used to help support the participant towards achieving his or her physical activity and sedentary behavior lifestyle goals.

(iii) After study completion, participants will be asked to complete a follow-up interview in person during the end of study follow-up (month 6). The interview will take no longer than 15-20 minutes. The conversations may be recorded only with the participant's permission. Once the audio recordings are transcribed, the audio recordings will be immediately destroyed.

Table 2. Self-completed Measures (1 – 1.5 hours)

Measure	Baseline	Month 4 follow up	Month 6 follow up
General Health and Health Related Quality of Life	✓		
Perceived Competence Scale for Participating in	✓	✓	✓

Regular Physical Activity			
Short Health Care Climate Questionnaire	✓	✓	✓
Exercise Self-Regulation Questionnaire	✓	✓	✓
Basic Need Satisfaction in Relationships Scale	✓	✓	✓
Diet	✓	✓	✓
Activity Monitoring	✓	✓	✓

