After completing the measurements in Table 1, participants will be given questionnaires and small activity monitors. It will take approximately 1-1.5 hours to complete the questionnaires. A research staff member will collect the questionnaires from the participant after a week.

1. Perceived Competence Scale for Participating in Regular Physical Activity: This is a 4-item questionnaire that assesses a participant's feelings of competence about engaging in physical activity.
2. Short Health Care Climate Questionnaire: This questionnaire has 6 items that assess a participant's perceptions of the degree to which the companion is supportive of autonomy; i.e., that the Companion considers the participants perspective and provides appropriate and meaningful feedback and opportunities for choice.
3. Exercise Self-Regulation Questionnaire: This is a 31- item self-report to measure the ability of the participant to regulate behavior to achieve one's goals
4. Basic Need Satisfaction in Relationships Scale: This scale addresses need satisfaction in general in one's life. It has 21 items assessing the three needs for competence, autonomy, and relatedness.
5. Diet: The participant will report frequency and portion size of foods consumed during the past month from a list of 70 commonly consumed food items on a questionnaire.
6. Activity Monitoring: physical activity measurement will be conducted in two ways. Firstly, using a thigh worn monitor. This measurement will be conducted for a period of 7-days at baseline and after 4 and 6 months. For this measurement the participant will wear 1 small lightweight (\approx 0.5 ounces) activity monitor (activPAL3TM, PAL Technologies, Glasgow, UK; product specs: <http://www.palt.com/pals/>) on his or her dominant thigh, which will be adhered to his or her skin using a hypoallergenic medical grade tape (3M TegadermTM Film, 3M, Minneapolis, MN; product specs: https://www.3m.com/3M/en_US/company-us/all-3m-products/~/3M-Tegaderm-Transparent-

Film-Dressing/?N=5002385+3293321979&preselect=3293786499&rt=rud). During the 7-day measurement periods, the participant will also complete a record of times the monitors were removed from his or her person. These thigh sensor data will not be transmitted wirelessly. The researchers will download the data from the devices upon collecting them from the participants. The researchers will go to the participant's office/home to collect these.

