Participants in the lifestyle physical activity intervention group will also have the battery life of his or her wrist-worn activity monitor frequently monitored by the researchers via the passive data transfer system. When the researchers detect that the device has a low battery (battery life is approximately 2-3 weeks), the participant will be prompted to schedule a time to receive a new device from the researchers. The researcher will go to the participant's office or home to collect the monitor and return it charged by the next day to commence the daily physical activity measurement.

We will encourage participants in both groups to wear the sensors as much as possible so that: 1) we may be able to understand the differences in daily/weekly physical behavior change effects between the two intervention approaches, and 2) we may be able to tailor daily recommendations of participants in the lifestyle physical activity intervention group to maximize and maintain his or her gains and to help meet his or her goals. Participants may remove the sensors for brief intervals throughout the day (e.g., for showering). The researchers may provide participants in the lifestyle physical activity intervention group with retrospective feedback of his or her physical activity measurements via text-message frequently (4 to 7 times a day at intervals of 1 to 4 hours between 7

am – 10 pm), following the virtual session (Table 1 #8). To reiterate, daily retrospective feedback (health coaching) will last for 4 months, concluding at the month-4 follow up.

Change in outcome measurements will be provided to participants after the follow up at month 6, when requested by the participant.

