9.4.9 EXPLORATORY ANALYSES

Random intercept mixed linear models that account for repeated measures will be used to analyze exploratory outcomes. Results will be presented as Least-squares means (LSMEANS) with 95% confidence intervals. Effect sizes and confidence intervals will be calculated for all comparisons.^{23,24} Analyses for exploratory outcomes will be considered to be hypothesis-generating and thus, will not be adjusted for multiple testing (i.e., $\alpha = 0.05$). Effect sizes and confidence intervals will be calculated for all comparisons.^{23,24}

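### Autonomy support is measured with a questionnaire about the Companion, which nobody has met at baseline and controls never receive, so its planned comparison between arms cannot be interpreted

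*Combined protocol and SAP*

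**What the plan says.** The exploratory endpoints (Sections 1.1, 3 and 6.1.1) include autonomy support from the Companion and relatedness to the Companion. Section 8.1 describes the 6-item Short Health Care Climate Questionnaire as assessing "perceptions of the degree to which the companion is supportive of autonomy".

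Table 2 in Section 8.1 ticks the "Short Health Care Climate Questionnaire" at baseline, month 4 and month 6. It has visit columns and no arm column. The text below it reads: "After completing the measurements in Table 1, participants will be given questionnaires and small activity monitors".

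On exposure, Section 6.1.1 says of controls: "This group will not receive the Companion, which will be the only difference with the treatment group". In the treatment arm, Section 8.1 places the text-message feedback after the virtual session held 7 to 14 days after baseline, and says that the coaching "will last for 4 months, concluding at the month-4 follow up".

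On analysis, the Aim 2 hypothesis in Section 4.1 is: "The treatment group will show greater improvements in health and psychosocial outcomes than controls after 16 and 24 weeks". Section 9.4.9 states: "Random intercept mixed linear models that account for repeated measures will be used to analyze exploratory outcomes". Section 9.4.1 allows adjustment for the outcome's baseline value where necessary. No section makes an exception for outcomes that refer to the Companion.

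**The concern.** A comparison of improvement between arms needs the same quantity to be measured in both arms and at both ends of the change. A questionnaire that asks how far the Companion supports autonomy does not meet that condition when one arm never has a Companion and the other does not yet have one at baseline.

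A respondent without a Companion can leave the items blank, guess, or answer about someone else, most plausibly the trainer. Blanks of this kind are not losses to follow-up, so the missing-at-random assumption in Section 9.4.1 does not cover them. Answers about the trainer would mean that the two arms rate different things. In each case the estimated arm effect would largely reflect whether the respondent had a Companion to rate, and not a difference in perceived support.

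The second exploratory objective in Section 3 is to examine mediators and moderators of behaviour change. If this scale is used as a mediator, the same problem carries over.

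**Working it through.** The plan gives no figure to reproduce. The check traces each psychosocial scale in Section 8.1 to what it asks about, who can answer it and when, and then counts administrations.

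**Step 1. What each scale refers to, as Section 8.1 describes it**

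| Scale | Refers to | Answerable at baseline and by controls? |
|---|---|---|
| Short Health Care Climate | The Companion | No |
| Basic Need Satisfaction in Relationships | Needs met in life generally | Yes, but the endpoint is labelled as relatedness to the Companion |
| Perceived Competence | The participant's own physical activity | Yes |
| Exercise Self-Regulation | The participant's own behaviour | Yes |

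One of the four scales lacks a referent. A second has a referent that differs from its endpoint label. Two have no problem.

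**Step 2. Who completes the questionnaire.** Section 8.1 names the arm wherever a procedure differs between arms (counselling, wrist devices, text feedback). It does not do so for the questionnaires, so the ordinary reading is that both arms receive them. This is an inference.

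**Step 3. Who has experienced the Companion at each visit.** Controls: at no visit. Treatment arm: not at baseline, because messaging follows the day 7 to 14 session; at month 4, yes; at month 6, only in retrospect, because coaching ends at month 4. Section 6.1.1 speaks of Companion communication in weeks 1 to 4 without saying from which day weeks are counted. I follow Section 8.1, which gives the order explicitly.

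**Step 4. Count.** Inputs: 46 participants, 23 in treatment (Section 1.1), hence 46 − 23 = 23 controls; three visits (Table 2).

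- Planned administrations: 46 × 3 = 138.
- Controls without a referent: 23 × 3 = 69.
- Treated participants without a referent, baseline only: 23 × 1 = 23.
- Total: 69 + 23 = 92, and 92 / 138 = 0.667, or 67%.

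**Step 5. Sensitivity to the inputs.** Simple randomization (Section 6.3) does not guarantee equal arms. With *t* treated, the count is 3(46 − *t*) + *t* = 138 − 2*t*. For *t* = 20 it is 98 (71%); for *t* = 26 it is 86 (62%). If controls were in fact not given the questionnaire, the count would be 23 of 23 × 3 = 69 (33%), all at baseline. There would then be no control data with which to make the Aim 2 comparison.

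**Step 6. Set against the analysis.** Aim 2 compares change from baseline between arms. For autonomy support, the baseline has no referent in either arm and the control follow-up has none. Only the treated values at months 4 and 6 have a clear meaning, and these alone give neither a change nor a contrast.

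**The case against.** The strongest reply is that the documents contain only a one-sentence description of the questionnaire and not the form. Controls also have trainers and counselling researchers, so their version might be worded around those people, and nothing says outright that controls complete it. That is fair. It is why the count is conditional on the ordinary reading of Section 8.1. It does not remove the point, since no alternative referent, not-applicable code or treatment-only analysis is written down, and the baseline problem in the treatment arm remains under either reading.

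A reader might infer that the whole psychosocial comparison in Aim 2 fails. The documents do not support that: perceived competence and exercise self-regulation concern the participant and can be compared between arms at every visit. Nor do they support saying that controls cannot answer the relatedness scale. As described it is a general scale, and the fault lies in the endpoint label.

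The consequences for baseline adjustment and mediation are also conditional. Section 9.4.1 adjusts for baseline only where necessary, Section 3 names no mediators, and Section 9 specifies no mediation model.

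Finally, Section 9.4.9 treats these outcomes as hypothesis-generating. This limits the importance of the point. It justifies leaving multiplicity unadjusted, but it does not give meaning to a contrast that has none.

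**Conclusion.** The point holds for one exploratory endpoint, with a separate labelling fault in a second. As written, the Aim 2 comparison of autonomy support between arms cannot be interpreted, and the same applies to any baseline adjustment or between-arm mediation analysis that uses this scale. About two thirds of the questionnaire's planned administrations (92 of 138) lack a referent. This assumes that both arms complete it, that arms are 23 each, and that Companion messaging starts after the virtual session. The endpoint of relatedness to the Companion is not what its listed scale is described as measuring.

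The other two psychosocial scales stand. The primary endpoint and the sample size, which rests on HbA1C, do not depend on this questionnaire. The point is worth correcting because the stated analysis would yield an estimate without a clear meaning, and because questionnaire wording cannot be repaired once the data are collected.

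**What to change.** Choose one of two options for autonomy support and state it in Sections 8.1 and 9.4.9:

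1. Word the questionnaire around something both arms have, such as the trainer or study staff, rename the endpoint accordingly, and keep the comparison between arms.
2. Give the Companion-worded version only to the treatment arm at months 4 and 6, report it descriptively (noting that the month 6 rating is retrospective), and remove it from the Aim 2 contrast and from any between-arm mediation analysis.

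In either case, state which arms complete each questionnaire in Table 2, and relabel the relatedness endpoint in Sections 1.1, 3 and 6.1.1 to match its general scale.

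The cost is a change to the questionnaire instructions, the endpoint labels and a short addition to the analysis text. Option 1 no longer measures support from the Companion itself. Option 2 gives up a between-arm test of Companion-specific autonomy support.

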8.2 SAFETY ASSESSMENTS

During the group exercise sessions, participants will be informed that if they feel tired or are uncomfortable to please tell the researchers and the session will be stopped or resumed after a break.

As participants will have been fasting (no food or beverage other than water) for 12 hours prior to outcome measurement, participants will be asked if they are feeling physically alright and will be offered a snack after the finger-stick blood measure. They will be thereafter instructed to resume their regular diet. Participants will also be encouraged to bring their own food if they prefer when testing in the laboratory.

Individuals with skin allergies or skin sensitivities to adhesive tape will be excluded from the study. Tape is required to adhere sensors to the skin to measure the primary outcome.

Should the participant score low on cognitive function test they will be asked if they would like to be provided with a resource handbook for dealing with cognitive dysfunction. The handbook is a publicly available resource from the New York public health department containing various strategies for addressing different forms of cognitive dysfunction, and also provides external resource lists.

8.3 ADVERSE EVENTS AND SERIOUS ADVERSE EVENTS

8.3.1 DEFINITION OF ADVERSE EVENTS

Adverse (AE) and Serious Adverse Events (SAE) will be defined per guidelines from the Office of Human Research Protections (OHRP) of the Department of Health and Human Services.

An adverse event is any untoward medical occurrence in a participant, whether or not it is causally related to the study.

8.3.2 DEFINITION OF SERIOUS ADVERSE EVENTS

A serious adverse event is any experience that results in any of the following outcomes: death, is life threatening, inpatient hospitalization or prolongation of hospitalization, a persistent or significant disability/incapacity. Important medical events that may not result in death, be life-threatening, or require hospitalization may be considered a serious adverse event when, based upon appropriate medical judgment, they may jeopardize the patient or participant and may require medical or surgical intervention to prevent one of the outcomes listed in this definition.

8.3.3 CLASSIFICATION OF AN ADVERSE EVENT

8.3.3.1 SEVERITY OF EVENT

- Mild: Awareness of a sign or symptom but easily tolerated.
- Moderate: Discomfort sufficient to cause interference with usual activity or to affect clinical status.
- Severe: Incapacitating with inability to do usual activity or to significantly affect clinical status.
- Life Threatening: The participant was at immediate risk of death from the adverse event as it occurred.

8.3.3.2 RELATIONSHIP TO STUDY INTERVENTION/EXPERIMENTAL MANIPULATION

All AEs will have their relationship to study intervention or study participation assessed with a level of specificity appropriate to the study design. The clinician's assessment of an AE's relationship to study intervention (drug, biologic, device, behavioral) is part of the documentation process, but it is not a factor in determining what is or is not recorded in the study. Describe the method of determining the relationship of an AE to a study intervention. If there is any doubt as to whether a clinical observation is an AE, the event should be recorded. Some protocols may use a binary assessment (related/not related); others may have a scale of relatedness. Evaluation of relatedness must consider etiologies such as natural history of the underlying disease, concurrent illness, concomitant therapy, study-related procedures, accidents, and other external factors. In a clinical trial, the study intervention must always be suspect.

The Investigator will also assess the relationship of any adverse event to study, based upon available information, using the following guidelines:

- 0 = Unlikely: No temporal association, or the cause of the event has been identified.
- 1 = Possible: Temporal association, but other etiologies are likely to be the cause; however, involvement of the study procedures cannot be excluded.
- 2 = Probable: Temporal association, other etiologies are possible, but not likely.

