8.3.4 TIME PERIOD AND FREQUENCY FOR EVENT ASSESSMENT AND FOLLOW-UP

All adverse events that are both serious and unexpected will be reported by the pilot PI and the Roybal Center PI to the IRB's, NIA PO and to the Safety Officer, within 48 hours of the study's knowledge of SAE. The summary of all other SAEs will be reported to NIA PO and to the Safety Officer, quarterly, unless otherwise requested by the Safety Officer.

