8.4 UNANTICIPATED PROBLEMS

8.4.1 DEFINITION OF UNANTICIPATED PROBLEMS

Unanticipated problems are those that:

- Are unexpected in terms of nature, severity, or frequency, given (a) the research procedures that are described in the protocol-related documents and (b) the characteristics of the study population;
- Are related or possibly related to participation in the research suggest that the research places participants and others at greater risk of harm than was previously known or recognized

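### As worded, relatedness grade 0 (Unlikely) in 8.3.3.2 takes in events whose established cause is the study itself, and no higher grade fits them

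*Combined protocol and SAP*

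**What the plan says.** Section 8.3.3.2 gives three grades for the relationship of an adverse event to the study. The bottom of the scale is worded "0 = Unlikely: No temporal association, or the cause of the event has been identified". The top of the scale, with no grade above it, is worded "2 = Probable: Temporal association, other etiologies are possible, but not likely". Between them lies the grade Possible, for an event with a temporal association where other causes are likely but a role of the study procedures remains open.

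The same section lists the etiologies to be weighed, among them "concurrent illness, concomitant therapy, study-related procedures, accidents, and other external factors". It also states that "In a clinical trial, the study intervention must always be suspect", and says of the relatedness assessment that "it is not a factor in determining what is or is not recorded in the study".

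Relatedness reappears in 8.4.1, where one condition for an unanticipated problem is that events "Are related or possibly related to participation in the research". The documents do not say which of the grades 0 to 2 satisfy that condition.

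**The concern.** A causality scale should move up as the evidence for a study cause gets stronger. Here the second limb of grade 0 depends on whether a cause is known, not on what the cause is. An investigator who applies the words as they stand would give the lowest grade to the cases in which the study's role is plainest.

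The causality record for those events would then be wrong. For an event that is also unexpected, a grade of Unlikely could be taken to mean that it fails the relatedness condition in 8.4.1 and so is not an unanticipated problem. The setting makes such events plausible: section 2.3.1 names exercise injury, muscle soreness and skin reactions to sensors as risks, and section 8.1 includes push-up and squat tests taken to exhaustion or voluntary stop.

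**Working it through.** No arithmetic applies, and the plan states no figure to reproduce. The check is whether each grade's wording fits one defined case.

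**Test case.** A muscle strain during the squat test in 8.1. The timing fits, the test is identified as the cause, and other explanations have been excluded. (The case is constructed for the check; it does not come from the documents.)

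| Grade | What the wording requires | Does the case meet it? |
|---|---|---|
| 0, Unlikely | No temporal association, *or* an identified cause | Yes, through the second limb |
| 1, Possible | Temporal association, with other causes likely | No: other causes are not likely |
| 2, Probable | Temporal association, with other causes possible but not likely | Not literally: other causes are excluded |

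**Can an identified cause be the study?** Yes, on the section's own terms. Its list of etiologies to consider includes study-related procedures. Grades 1 and 2 both refer to etiologies *other* than the study; grade 0 drops that qualifier.

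**Behaviour along the scale.** Hold the timing fixed and strengthen the evidence for a study cause:

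1. Other causes likely, study not excluded: grade 1.
2. Other causes possible but not likely: grade 2.
3. Other causes excluded, study cause established: grade 0 by the words.

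The sequence 1, 2, 0 is not monotone, and the break falls at the last step.

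**Where a wrong grade would have an effect.**

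- *Recording:* none. Section 8.3.3.2 says relatedness does not decide what is recorded.
- *Expedited reporting of serious events:* none. The 48-hour trigger in 8.3.4, repeated in 8.3.5, is "All adverse events that are both serious and unexpected will be reported by the pilot PI and the Roybal Center PI", with no relatedness condition.
- *General adverse event reporting:* none. The opening of 8.3.5 sends adverse events to the IRBs, the funder's program officer and the Safety Officer without a relatedness filter.
- *Unanticipated problems:* possible. 8.4.1 includes a relatedness condition. However, 8.4.2 sends the reporting of such problems back to 8.3.5, so the recipients are the same. What could be lost is the classification.
- *Safety tabulations:* none planned. Section 9.4.4 (safety analyses) is marked not applicable, and 10.1.6 mentions standardized reports without specifying any table by relatedness.

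**The case against.** The best defence is that the clause should be read within its scale. The grades are guidelines on the relationship to the study, the label is Unlikely, and the neighbouring grades are framed around other etiologies. In that setting an identified cause most naturally means an alternative cause, and the sentence that the intervention must always be suspect points the same way. A sensible investigator would probably grade a clear study-caused event 2, since an event with no other cause satisfies *not likely* all the more strongly.

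Most of this stands as an account of intent. It does not repair the text: the general sentence on suspicion does not amend grade 0, and nothing else in the section says which cause is meant.

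Three stronger readings are tempting, and the documents support none of them.

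- A reader might infer that study-caused harms would go unreported. Recording and the 8.3.5 routes do not use relatedness, so they would not. The risks named in 2.3.1 are also expected in their usual form, so they would not normally be unanticipated problems whatever their grade.
- A reader might infer that such events would be filed as unrelated, or that published or Safety Officer counts would understate harm. The lowest label is Unlikely, there is no unrelated grade, and no count by relatedness is planned.
- A reader might infer that a Definite grade is required. Stopping at Probable is a legitimate choice, provided that grade 2 is worded to include established study causes.

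**Conclusion.** The point holds as a minor wording defect. By its words, grade 0 covers any event with an identified cause, including a study cause, and grade 2 does not literally cover an event for which other causes are excluded. An event with an established study cause therefore fits only the lowest grade.

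The consequence is confined to the causality record and to the classification of unexpected events under 8.4.1. That second effect assumes that a grade of Unlikely would be treated as failing the relatedness condition; this is a natural inference, but the documents do not state it. How many events would be affected cannot be derived from the documents. No endpoint, analysis or reporting deadline is touched.

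**What to change.** Make three changes to the text:

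1. In 8.3.3.2, reword grade 0 as: *No temporal association, or a cause other than the study intervention or study procedures has been identified.*
2. In 8.3.3.2, widen grade 2 so that it covers events for which other etiologies are unlikely or have been excluded. Adding a separate Definite grade would do the same job.
3. In 8.4.1, state that every grade above 0 meets the relatedness condition.

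The cost is a few lines of protocol text, plus one extra option on the adverse event form if a Definite grade is chosen. Data collection is otherwise unchanged.
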